
Proprietary confidential information.

© 2016 Boehringer Ingelheim International GmbH or one or more of its affiliated companies. All rights reserved.

This document may not - in full or in part - be passed on, reproduced, published or otherwise used without prior written permission.

if a patient is willing to return to the pre-defined study visits, with exception of collection of adverse events, outcome events, concomitant therapy and laboratory testing of creatinine for the calculation of the eGFR.

If a patient who prematurely discontinued study drug is not willing to return to the pre-defined study visits, at minimum a yearly telephone call (preferably every 6 months) and a telephone call at study end will be required, to document the occurrence of outcome events and vital status. If possible, other AE's and concomitant therapy changes since last visit might be recorded. Every attempt will be made by the investigator to ensure patients continue participating in the study during study drug interruptions and after discontinuation of study drug. The ITT analysis requires that all study patients be followed until study end even if the study drug was temporarily interrupted or discontinued.

Patients will have a follow up visit ~~one week~~ **30 days** following regular or premature completion of the treatment period. The follow-up visit may be performed as a phone visit for patients who did not prematurely discontinue study medication and who do not have abnormalities at the EOT visit (only AEs/outcome events and changes in concomitant therapy to be obtained).

In case early study termination is to be performed (e.g. based on recommendation by the Data Monitoring Committee [DMC]), a reasonable timeframe to stop the trial (perform last patient visits) will be defined and communicated to the investigators.

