**Early discontinuation of study medication is not a criterion for withdrawal of consent for participating in the study.**

If a patient becomes pregnant during the trial, the study treatment will be stopped, the patient will be followed up during the study and until birth or termination of the pregnancy (see further details in [Section 5.2.2.2](#)).

If pancreatitis is suspected, the study treatment should be stopped.

**An individual patient is to be withdrawn from the study and follow up assessments only if the patient actively withdraws consent, without the need to justify the decision.**

Proprietary confidential information.

© 2016 Boehringer Ingelheim International GmbH or one or more of its affiliated companies. All rights reserved.

This document may not - in full or in part - be passed on, reproduced, published or otherwise used without prior written permission.

A patient has the right to withdraw informed consent for participation at any time for any reason. However, withdrawal of consent from study participation should be very rare and unusual. Because of this, the investigator should be involved in the discussions with the patient regarding a withdrawal of consent. Additionally, the investigator should discuss the withdrawal of consent with the sponsor representative prior to stopping study participation.

Patients that are not actively taking study drug may be less motivated to adhere to the study visit schedule. Investigators and site staff should work to detect early signs of losing interest and readily present such patients (not actively taking study drug) with the following options to encourage continued participation:

- Option 1 Continue to attend regularly scheduled study visits at the site until the study ends
- Option 2 Conduct all remaining study visits over the phone
- Option 3 Discontinue participation in remaining study activities but permit collection of vital status and CV outcome events at minimum at the end of the study through the patient or alternative person designated by the patient (e.g., family, spouse, partner, legal representative, or physician) even if only by telephone
- Option 4 Discontinue participation in remaining study activities but permit collection of vital status at minimum at the end of the trial through the patient, alternative person designated by the patient, or through review of patient's medical information from alternative sources (e.g., doctor's notes, hospital records, etc.)

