#### 5.2.2.2 Adverse event and serious adverse event reporting

**The Investigator shall maintain and keep detailed records of all AEs in their patient files.**

All adverse events, serious and non-serious, occurring during the course of the clinical trial (i.e., from signing the informed consent onwards through the last per protocol visit) will be collected, documented and reported to the sponsor/CRO by the investigator on the appropriate CRF(s) / eCRFs / SAE reporting forms. The investigator does not need to actively monitor patients for adverse events once the clinical trial has ended. However, if the investigator becomes aware of an SAE(s) that occurred after the last per protocol visit, it should be reported by the investigator to the sponsor if considered relevant by the investigator. Reporting will be done according to the specific definitions and instructions detailed in the 'Adverse Event Reporting' section of the Investigator Site File.

For each adverse event, the investigator will provide the onset date, end date, intensity, treatment required, outcome, seriousness, and action taken with the investigational drug. The investigator will determine the relationship of the investigational drug to all AEs as defined in Section 5.2.2.1.

The investigator must report the following events, immediately (within 24 hours of awareness) to the sponsor/CRO: SAEs, AESI and non-serious AEs relevant for the reported SAE or AESI.

The investigator must document immediately (within 24 hours of awareness) CV outcome events if they occur after randomization on the appropriate eCRF page. CV outcome events which occur prior randomization have to be reported as an (S)AE.

Clinically relevant abnormalities found at physical examination, vital signs or ECG that are not pre-existing prior to signing of informed consent (study inclusion) should be reported as adverse events. If such abnormalities already pre-exist prior to signed informed consent they should be considered as baseline conditions.

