**AEs considered "Always Serious"**

Proprietary confidential information.

© 2016 Boehringer Ingelheim International GmbH or one or more of its affiliated companies. All rights reserved.

This document may not - in full or in part - be passed on, reproduced, published or otherwise used without prior written permission.

**Cancers of new histology and exacerbations of existing cancer must be reported as a serious event regardless of the duration between discontinuation of the drug and the occurrence of the cancer. In accordance with the European Medicines Agency initiative on Important Medical Events, Boehringer Ingelheim has set up a list of further AEs, which by their nature, can always be considered to be “serious” even though they may not have met the criteria of an SAE as given above.**

**The latest list of “Always Serious AEs” can be found in the ISF. A copy of the latest list of “Always Serious AEs” will be provided to you upon request. These events should always be reported as SAEs as described above.**

BI has set up a list of AEs which are defined to be always serious. In order to support the investigator with the identification of these “always serious adverse events”, if a non-serious AE is identified to be serious per BI definition, a query will be raised. The investigator must verify the description and seriousness of the event. If the event description is correct, the item “serious” needs to be ticked and an SAE has to be reported in expedited fashion following the same procedure as above.

~~The list of these adverse events can be found in the ISF.~~

*For Japan: This information must be also reported immediately to the head of the trial site.*

With receipt of any further information to these events, a follow-up SAE report has to be provided. SAEs, **AESIs** and non-serious AEs must include a causal relationship assessment made by the investigator. The SAE form is to be forwarded to the defined unique entry point (contact details will be provided in the Investigator Site File). This immediate report is required irrespective of whether the investigational product has been administered or not and irrespective of causal relationship. It also applies if new information to existing SAEs or Adverse Events of Special Interest becomes available.

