**Early discontinuation of study medication is not a criterion for withdrawal of consent for participating in the study.**

### 6.2.3 End of treatment and follow-up period

**Patients who discontinue study drug should continue study visits until study end. Study assessments may be omitted if a patient is willing to return to the pre-defined study visits, with exception , collection of adverse events, outcome events, concomitant therapy and laboratory testing of creatinine for the calculation of the eGFR.**

**If a patient who discontinued study drug is not willing to return to the pre-defined study visits, at minimum a yearly telephone call (preferably every 6 months) and a telephone call at study end will be required, to document the occurrence of outcome events and vital status. If possible, other AE's and concomitant therapy changes since last visit should be recorded. Every attempt will be made by the investigator to ensure patients continue participating in the study during study drug interruptions and after discontinuation of study drug.**

**Patients that are not actively taking study drug may be less motivated to adhere to the study visit schedule. Investigators and site staff should work to detect early signs of losing interest and readily present such patients (not actively taking study drug) with options to encourage continued participation. Refer to [section 3.3.4.1](#) for options to encourage continued participation and for details regarding patients who are lost-to-follow-up or who have withdrawn informed consent.**

~~If the patient withdraws informed consent for study participation, the study participation of the patient will end. The patient should stop taking study medication and should be asked to complete the EOT and follow up visit activities as described in the [Flow Chart](#). Completing these procedures is strongly recommended for the patient's safety.~~

Proprietary confidential information.

© 2016 Boehringer Ingelheim International GmbH or one or more of its affiliated companies. All rights reserved.

This document may not - in full or in part - be passed on, reproduced, published or otherwise used without prior written permission.

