#### 7.8.1.1 Assignment of AEs to treatment

The analysis of AEs will be based on the concept of treatment-emergent adverse events (TEAE). That means that all AEs occurring between first study drug intake until 7 days after last permanent study drug stop will be considered as on-treatment, i.e. possible treatment interruption phases of a patient will be part of the on-treatment phase.

All AEs occurring prior to first study drug intake will be assigned to "screening". All AEs occurring after last study drug intake + 7 days will be assigned to "post-treatment", whereby the post-treatment phase according to the previous treatment will be used (post-Lina and post-Placebo respectively). AEs reported after the date of last contact + 1 day will be assigned to "post-study".

Patients who died before last drug intake + 7 days will have their on-treatment phase assigned until the date of death.

In addition to the primary treatment emergent approach displaying the on-treatment phase and post-treatment phase separately, all AEs after the first dose of study medication will be included in an additional analysis by treatment group.

Further additional approaches will be implemented for the presentation of adverse events:

• For cancer and pancreatic cancer in addition to the 'TEAE approach' on the treated set, all adverse events that occurred between first study drug intake up to study end will be presented.

There will be additional analyses including all patients who had a minimum cumulative study drug exposure of 6 months (excluding treatment gaps), using following two approaches:

- o considering all AEs starting from the date when 6 months cumulative exposure was reached up to last drug stop + 7 days
- o considering all AEs starting from date when 6 months cumulative exposure was reached up to individual day of trial completion
- For renal events, hepatic events, pancreatitis and skin lesions all adverse events that occurred between first study drug intake up until treatment stop + 30 days will be presented based on the treated set.
- Heart failure adverse events (based on narrow SMQ cardiac failure 20000004) will be analyzed following the 'TEAE approach' (all AEs occurring between first study drug intake until 7 days after last permanent study drug stop will be considered as ontreatment) and the concept where all AEs from first study drug intake up to study end are assigned to treatment.

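### For patients off drug who refuse visits, the required telephone calls need not ask about non-cardiovascular SAEs, cancer or pancreatitis, although Protocol 5.2.2.2 requires their collection and the SAP tabulates several of them to study end

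*Protocol*

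**What the plan says.** **The minimum call.** For a patient off study drug who will not return to visits, Protocol 6.2.3 sets this contact: "at minimum a yearly telephone call (preferably every 6 months) and a telephone call at study end will be required". Its purpose is "to document the occurrence of outcome events and vital status". On all other events the text is "If possible, other AE's and concomitant therapy changes since last visit should be recorded". Section 3.3.4.1 and flow chart footnote C carry the same rule with *should*. Section 3.1 is weaker: "If possible, other AE's and concomitant therapy changes since last visit might be recorded".

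**Reduced options.** Section 3.3.4.1 offers four levels of continued participation. Option 2 keeps all remaining visits, by telephone. Under Option 3 the patient leaves other study activities but agrees to "permit collection of vital status and CV outcome events at minimum at the end of the study". Option 4 covers vital status only.

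**The AE rule.** Section 5.2.2.2 states that all AEs, serious and non-serious, "from signing the informed consent onwards through the last per protocol visit) will be collected, documented and reported", with no exception for telephone follow-up. It adds that new or worsening cancers "must be reported as a serious event regardless of the duration between discontinuation of the drug and the occurrence of the cancer".

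**The analyses.** For cancer and pancreatic cancer, SAP 7.8.1.1 adds to the treatment-emergent approach that "all adverse events that occurred between first study drug intake up to study end will be presented". SAP 7.8.1.8 (adjudicated pancreatic events) and 7.8.1.9 (oncology-committee events) also run from treatment start to study end on the Treated Set.

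**The concern.** A site can follow the call rule to the letter and not ask about a cancer diagnosis or a late pancreatitis admission. The patient then enters the to-study-end tables with no event recorded. Cancer is the harm for which time off drug matters most, because of its latency, and the extended SAP windows exist to use that time.

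If the telephone-only group is sizeable, the cancer, pancreatic and oncology-committee counts will be too low. If it is larger in one arm, the comparison between arms is distorted as well.

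There is a related ambiguity for the key secondary endpoint. The calls cover outcome events, but the only definition the protocol gives is for cardiovascular outcome events. Whether the caller must ask about dialysis or transplant is left unstated.

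**Working it through.** The check is mainly a comparison of texts. The plan gives no figure to reproduce.

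**1. What counts as an outcome event?** The only list is in Protocol 5.2.1.1. It covers CV death, MI (including silent MI), stroke, hospitalisation for unstable angina or heart failure, TIA, and coronary and peripheral revascularisation. Cancer, pancreatitis and SAEs in general are not on it. Section 5.2.2.1 lists pancreatitis, pancreatic cancer and thyroid cancer as AESIs. At the minimum call these are therefore other AEs, recorded if possible.

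**2. Can the call rule and 5.2.2.2 both be met?** One attempt is to say that the last per protocol visit of a visit-refuser is the last one attended, so collection has ended. The protocol does not define the term for such a patient. Even on that reading the cancer rule has no time limit, and the SAP windows still run to study end. Section 3.3.4.1 also wants patients off drug observed as though still on blinded treatment, which an optional AE enquiry does not achieve.

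**3. Does expedited reporting close the gap?** Only in part. SAEs and AESIs are due within 24 hours of awareness (5.2.2.2). That duty begins when the site knows of the event, and the minimum call does not oblige the site to find out.

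**4. Which analyses are exposed?**

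| Analysis | Window | Exposed? |
|---|---|---|
| Primary 3-point MACE | to trial completion | No: outcome events and vital status are required at the call |
| Main AE analysis (SAP 7.8.1.1) | drug stop + 7 days | No |
| Investigator-reported pancreatitis (SAP 7.8.1.1) | treatment stop + 30 days | Little: a follow-up visit with AE collection is planned 30 days after stopping |
| Cancer and pancreatic cancer, additional (SAP 7.8.1.1) | to study end | Yes |
| Adjudicated pancreatic events (SAP 7.8.1.8) | to study end | Yes |
| Oncology-committee events (SAP 7.8.1.9) | to study end | Yes |

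One cancer analysis, in patients with at least 6 months' cumulative exposure, runs to the individual day of trial completion. Under SAP 6.8.3 the last telephone contact counts towards that day. A call at which cancer was never raised can therefore extend event-free follow-up.

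**5. Illustrative size (assumed values).** Let f be the share of to-study-end person-time that is telephone-only, and s the fraction of events captured there. Neither is in the documents.

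Observed rate = true rate × [1 − f(1 − s)], so the under-count is f(1 − s).

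- f = 5%, s = 0.8: 0.05 × 0.2 = 1%.
- f = 20%, s = 0: 0.20 × 1 = 20%.

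The observed rate ratio is the true ratio × [1 − f₁(1 − s)] / [1 − f₂(1 − s)], taking s equal in both arms.

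- f₁ = f₂: the factor is 1, so the ratio is unchanged.
- f₁ = 15%, f₂ = 10%, s = 0.5: 0.925 / 0.950 = 0.974.
- f₁ = 15%, f₂ = 10%, s = 0: 0.850 / 0.900 = 0.944.

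**The case against.** Much can be said for the plan.

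- **Who is affected.** Stopping drug does not by itself lead to weaker follow-up. Patients who stop should keep attending, and AE collection is among the items that cannot be omitted at those visits. Option 2 preserves the visits by phone, and patients are asked to choose the fullest follow-up they will accept. The gap concerns visit-refusers only. This stands.
- **Pancreatitis.** A reader might infer that stopping drug for suspected pancreatitis moves those patients into weaker follow-up. The text does not support that. The event prompting the stop arises on drug, is an expedited AESI, and is followed by the 30-day visit. Only later pancreatic events in visit-refusers are exposed.
- **Heart failure.** The SAP also counts heart-failure AEs to study end, but hospitalisation for heart failure is a listed CV outcome event and so is within the required call.
- **Renal events.** It is tempting to say that Option 3 loses dialysis and ESRD. Option 3 is a minimum set by the patient, and the 6.2.3 calls refer to outcome events without limiting them to CV. Ambiguity is what the text shows.
- **SAP.** It nowhere claims complete collection; that is only implied by its windows. The extended analyses are supplementary and safety is descriptive. Parts of the SAP's censoring text are not public, so it cannot be said that the SAP has no rule for these patients.
- **Wording.** The amendment strengthened *might* to *should* elsewhere, so 3.1 looks like a missed edit.

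These points narrow the concern. None of them makes the minimum call ask about cancer or non-CV SAEs.

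**Conclusion.** The point holds as an inconsistency in current text with a limited consequence. Protocol 3.1, 3.3.4.1, 6.2.3 and flow chart footnote C make enquiry about non-CV SAEs, cancer and pancreatitis optional for visit-refusers off drug. Section 5.2.2.2 requires collection of all AEs through the last per protocol visit and cancer reporting without time limit. The supplementary to-study-end analyses of cancer, pancreatic cancer, adjudicated pancreatic events and oncology-committee events can be under-ascertained as a result.

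The size cannot be derived. The documents give no discontinuation rate, no share of telephone-only follow-up and no capture rate at the calls. A reader might multiply assumed rates into a number of missed cancers, but every input would be invented. The 1% to 20% range above only illustrates how the under-count depends on f and s. Nothing in the documents shows that the arms would differ, and without a difference the rate ratio is not biased. This is a cheap improvement worth making in a long-term safety study. It does not threaten the primary conclusion.

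**What to change.** **Protocol 3.1, 3.3.4.1, 6.2.3 and flow chart footnote C:**
- Make enquiry about SAEs and AESIs (cancer and pancreatitis named) and about renal outcome events (dialysis, transplant) a required item of the yearly and study-end calls.
- Keep the if-possible qualifier for non-serious AEs and concomitant therapy.
- Change *might* in 3.1 to *should*.

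**Option 3:** leave it as the patient's chosen minimum, and have sites request renal outcomes, SAEs and AESIs where the patient agrees. Making these compulsory would ask more of people who have already limited their participation, and could push some to Option 4 or full withdrawal at the expense of CV outcome data.

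**SAP:** for any to-study-end safety incidence rate, end time at risk at the last contact at which AEs were asked about. This does not alter the frequency tables in 7.8.1.8 and 7.8.1.9, which depend on the improved calls.

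**Cost:** amended protocol wording with the usual approvals, a few more questions in calls already required, slightly longer calls, and some late-reported SAEs to process. No extra visits are needed.

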## 7. STATISTICAL METHODS AND DETERMINATION OF SAMPLE SIZE

### 7.1 STATISTICAL DESIGN - MODEL

#### Design

This is a multicentre, multinational, randomized, double blind, parallel group, placebo-controlled safety study of linagliptin versus placebo. The trial is event driven and will run with an estimated number of 8300 **7000** randomized patients for an estimated period of 48 **54** months beginning with the randomization of the first patient. In case the number of events is not or may not be reached within this period the trial duration and/or the number of patients will be prolonged or increased respectively, to ensure that the required number of 625 **611** patients with adjudicated primary endpoint events is reached.

#### Objectives

The study objectives are described in [Section 2.2](#).

For the primary objective the upper bound of the two-sided (1-2\*alpha) confidence interval which equals the upper bound of the one-sided (1-alpha) confidence interval will be used to investigate non-inferiority (NI) of linagliptin versus placebo regarding the hazard ratio of the primary endpoint. The non-inferiority margin is chosen as 1.3 (FDA Guidance for Industry - Diabetes Mellitus - Evaluating Cardiovascular Risk in New Antidiabetic Therapies to Treat Type 2 Diabetes, ([R09-2151](#))). The overall one-sided significance level is 2.5%.

